### 5.2 Packaging and Labeling

The IMP will be labeled per each kit (container) with unique kit identifiers. Panzyga is delivered as ready-to-use solution in glass bottles. Placebo for intravenous infusion will be purchased and provided by Octapharma.

In order to prepare the infusion, IMP (Panzyga or placebo) is pooled into sterile and labeled infusion-bags (Polyvinyl Chloride (PVC)-free, Diethylhexylphthalate (DEHP)-free and latex-free). The IMP will be blinded with a labeled over-pouch (both the infusion bag and the over-pouch will be labeled). The blinded labels for infusion bags and over-pouches are provided below. Final labeling will be in compliance with the national requirements of each country where the study is to be conducted.

Each vial of Panzyga will be labelled as follows in the US:

Each bag of placebo will be labelled as follows in the US:

Proprietary Information

Blinding labels for infusion bags and over-pouches will be labelled as follows in the US:

Each vial of Panzyga will be labelled as follows in the EU:

Proprietary information. © 2023. All rights reserved.

Each bottle of placebo will be labelled as follows in the EU:

A large black rectangular redaction box covers the majority of the page below the text, starting just below the 'EU:' label and ending above the page number.

Property of Octapharma. Do not copy

Blinding labels for infusion bags and over-pouches will be labelled as follows in the EU:

### **5.3 Conditions for Storage and Use**

Panzyga should be stored and transported light-protected at +2 °C to +8 °C (36 °F to 46 °F) and must not be frozen. Panzyga must not be used after its expiration date.

Placebo solution should be stored and transported according to its product information between 2 °C (36 °F) and 25 °C (77 °F) and must not be frozen.

The authorized personnel will ensure that the IMP is stored in appropriate conditions with restricted access and in compliance with national regulations.

### **5.4 Dose and Dosing Schedule**

Panzyga is available in glass bottles with different volumes of human immunoglobulin. Glass bottles of different volume should be combined in order to reach the required amount of IgG, based on the IRT assignment.

Body weight will be measured at each visit once before each cycle prior to IMP administration and entered into the IRT, which will calculate the required IMP dose for both day 1 and day 2 infusions.

All patients should be clinically assessed for being adequately hydrated prior, during, and after IMP administration. Prophylaxis for TEEs should be considered for patients with risk factors for TEE or patients in the early phase of diagnosis as a precautionary measure. Please refer to Section 4.2.1.

The initial infusion rate will be █ mL/kg BW/min (█) and it may be progressively increased as tolerated by the patient also considering the tolerance level(s) of previous administrations [56]:

For infusion cycles 1 and 4 (when IMP is first given or switched at crossover [Figure 1]):

- █
- █
- █
- █

For infusion cycles 2, 3, 5, and 6 (when the same IMP is repeatedly administered during the same phase of the crossover design [Figure 1]):

- █
- █
- █
- █
- █

Importantly, the progressive increase in infusion rates is only intended in patients who can tolerate it. There is no obligation to increase the infusion rate to █ mL/kg BW/min in all patients. Assuming a maximum infusion rate of █ mL/kg BW/min, the duration of one infusion applied according to the rates described above is █ (hr:min). Patients must be observed for any symptoms at least once throughout the infusion period and at least one hour thereafter (Section 5.5). In patients at risk of thromboembolic adverse reactions and acute renal failure (such as hypertension, history of thrombotic episodes, patients with prolonged periods of immobilization, concomitant nephrotoxic medication, diabetes mellitus, overweight, hypovolemia), IMP should be administered at the minimum rate of infusion practicable.

The total dose for a single infusion cycle will be 2 g/kg BW (1 g/kg BW daily for two consecutive days). Patients will receive three infusion cycles at three-week intervals in the first phase of the study, followed by three additional infusion cycles at three-week intervals in the second blinded crossover phase of the study (patients previously in the Panzyga arm will be assigned placebo and patients previously in the placebo arm will be assigned Panzyga, administered at the same regimen).

If a patient is assigned placebo, the same volume and infusion rate as would have been applied in case of 2 g/kg BW Panzyga administration should be used. Therefore, placebo (0.9% w/v sodium chloride) will be administered at a dose of 20 mL/kg BW given over two consecutive days.

If AEs occur during the infusion, the infusion rate will be reduced to half the rate at which the event occurred, or the infusion will be interrupted until symptoms subside. The infusion may then be resumed at a rate tolerated by the patient. The administration of Panzyga 10% or sodium chloride 0.9% w/v must be completed within 8 hours after preparation. In case additional IMP is needed (e.g. lost or damaged), a separate IMP assignment via IRT transaction needs to be accomplished.

## 5.5 Preparation and Method of Administration

Each bottle of Panzyga and each bag of placebo must be examined visually by the site staff for particulate matter and discoloration prior to administration. Non-homogenous solutions or those that have a deposit must not be used.

IMP must be allowed to warm to room or body temperature prior to administration.

Patients must be monitored before IMP infusion, observed for any symptoms at least once throughout the infusion period and at least one hour thereafter.

Panzyga solution for IV infusion must not be mixed with other medicinal products or saline. For other IV products, a separate IV line must be used.

The special warnings and precautions for Panzyga use (see IB) must be followed

## 5.6 Blinding and Breaking the Study Blind

Study personnel blinded to treatment assignment will not have access to unblinded information until the study is formally unblinded.

The investigators will be provided with an unblinding procedure to disclose the actual treatment of a particular patient in case of medical emergency; this will be done through the IRT system.

To maintain blinding, infusions will be given in blinded infusion bags (corresponding to a volume of 2 g/kg BW Panzyga per cycle or placebo at each infusion day as tolerated by the patient, or by investigator's discretion).

The infusion bag is then blinded with a non-transparent over-pouch. The non-transparent over-pouch will be put over the infusion bag to maintain blinding. Both containers (infusion bag and over-pouch) will be re-labeled with a blinding label. The blinding label will be stuck on by the unblinded hospital pharmacist or designee.

The blinding labels will be identical for both Panzyga and placebo, so that the content of the bags is only known to the unblinded hospital pharmacist or designee. The unblinded hospital pharmacist or designee will send the infusion bag(s) per patient (potentially already fixed to the non-transparent infusion line) to the ward.

Infusion bags, over-pouches, labels, and non-transparent infusion lines/transparent lines with sleeves will be provided to the site.

To further ensure the blinded character of the study, the investigator or designee who applies the medication to the patient will not be involved in any other study procedures other than drawing blood samples or checking for vital signs, i.e. will not be involved in any patient ratings

or AE assessments. In an effort to protect the blinding of key efficacy ratings, the independent evaluator who completes clinician efficacy ratings (CY-BOCS) will not have knowledge of or access to adverse event reports.

The patient will be blinded with respect to study treatment throughout the study.

Emergency patient unblinding will be managed in the IRT system. In the event an investigator needs to unblind a study patient due to a medical emergency or for necessary medical reasons, authorized study personnel at the site will log into the IRT to request access to the unblinded randomization code for the patient in question. In order to do so, the investigator will have to acknowledge the serious circumstances that require unblinding. Upon taking these steps, the dedicated web-based system will then provide the investigator with the specific treatment arm for that patient. Upon finalization of the unblinding request, an email notification of this action will automatically be sent to appropriate management and safety officials acknowledging the patient unblinding without providing the specific treatment arm.

## 5.7 Treatment Compliance

### 5.7.1 Drug Dispensing and Accountability

Any IMP provided to the site will be accounted for. Unblinded Drug Accountability Logs will be kept current by the unblinded site staff, detailing the dates and quantities of IMP received and assigned to each patient, and the remaining quantity.

The logs will be available to the unblinded study monitor to verify drug accountability during the study.

Investigational medicinal product can be destroyed at the study site or returned to the Sponsor depot for destruction. If possible, the original vial/bottle and the unblinded label will be discarded only after study drug reconciliation by the unblinded study monitor. The unblinded study monitor confirms the verification of the usage as described in the IMP Handling Manual.

Unused and expired IMP will be verified by the unblinded study monitor and destruction or return has to be confirmed in writing by the Sponsor prior to the transfer of the product.

### 5.7.2 Assessment of Treatment Compliance

All patients will be infused at the study site under the surveillance of authorized study personnel. Infusion details will be documented together with the unique kit numbers and batch number(s) in the IRT system, which will be checked regularly by the unblinded study monitor.

## 6 STUDY CONDUCT

Patients and legal representative(s)/guardians(s) have to be informed about the study details and have to give their written informed consent/assent. If patients are old enough to understand the risks and benefits of the study (as determined by each institution), they should provide written assent/consent. A written informed consent must be obtained by the investigator or trained healthcare professional and signed by the investigator before the start of any screening activities.

Investigators must have received and reviewed the latest available laboratory results from the previous visit before initiating the next infusion cycle. Additionally, if a peripheral line is used for drawing blood, it must be flushed thoroughly.

[figure not shown]
Prior to randomization, patients will be screened for eligibility (inclusion and exclusion criteria) and to determine the baseline characteristics used for stratification (prophylactic use of antibiotics, treatment with stable dose of SSRIs during enrollment, and PANS/PANDAS disease subtype).

Screening procedures should be completed within 28 days before randomization. Based on the screening results, the patients' eligibility for the study is determined. To ensure the blinded character of the study, the investigator or designee who applies the medication to the patient will not be involved in any other study procedures other than drawing blood samples or checking for vital signs, i.e. will not be involved in any patient ratings or AE assessments.

The total time for the first study visit during an infusion cycle will be approximately 6-7 hours whereas the second infusion day will last for approximately 5 hours. Overnight stay at the study site between the two infusions will be at the discretion of the investigator.

6.1

## 6.1.1

- 
- 
- 
- 
- 
- 
- 
- 
- 
- 
- 
- 
- 
- 
- 
- 
- 
- 

### 6.1.3

### 6.1.4

Page 53 of 103

[figure not shown]
Property of Queen's University Belfast. Use is subject to written permission.

### 6.1.5

Property of the University of Hong Kong. Copying or distribution without written permission.

**6.1.6**

Property of Octapharma. Do not copy or distribute without permission.

• [REDACTED]  
[REDACTED]  
[REDACTED]

[REDACTED]

■ [REDACTED]

[REDACTED]

■ [REDACTED]  
[REDACTED]

■ [REDACTED]  
[REDACTED]

■ [REDACTED]  
[REDACTED]

■ [REDACTED]

■ [REDACTED]

6.1.7 [REDACTED]

[REDACTED]

[REDACTED]

■ [REDACTED] ■ [REDACTED] ■ [REDACTED] ■ [REDACTED] ■ [REDACTED] ■ [REDACTED] ■ [REDACTED]

■ [REDACTED]

■ [REDACTED]

■ [REDACTED]

■ [REDACTED] ■ [REDACTED]

■ [REDACTED]

■ [REDACTED]

■ [REDACTED]

6.1.8 [REDACTED]

[REDACTED]

[REDACTED] [REDACTED]

[REDACTED] [REDACTED] [REDACTED]

[REDACTED] [REDACTED] [REDACTED]

[REDACTED] [REDACTED] [REDACTED]

[REDACTED] [REDACTED] [REDACTED]

## 6.2 Duration of Study

### 6.2.1 Planned Duration for an Individual Patient

The duration of the first double-blind treatment phase (Panzyga vs. placebo) will be nine weeks. The duration of the second double-blind crossover phase will also be nine weeks. Thus, the overall study duration will be 18 weeks, plus up to 28 days from Screening to randomization

The study will be considered completed when all patients have completed the end of follow-up or Early Termination Visits.

### 6.2.2 Premature Termination of the Study

Both the investigator and the Sponsor reserve the right to terminate the study at any time. In this event, any necessary procedures for orderly study termination will be arranged after review and consultation by both parties. In terminating the study, the Sponsor and the investigator will ensure that adequate consideration is given to the protection of the patients' interests.

In addition to the ongoing safety monitoring and periodic IDMC data review, the following rule will be implemented to apply temporary suspension of study drug administration, pending a safety investigation, for an unacceptable increased venous TEE or acute renal failure risk in the Panzyga group compared to the placebo group:

- For both venous TEEs or acute renal failures, the event risk will be calculated separately as (number of events reported)/(number of infusions) in both randomization arms, and the 90% confidence interval for the resulting risk ratio ( $R_{Panzyga}/R_{Placebo}$ ) will be determined by means of the /relrisk option of the SAS procedure FREQ. In case no Events are observed in the placebo group, 1 will be added to each cell in the 2X2 table to enable this risk ratio evaluation. The stopping rule will be triggered if the lower confidence limit is greater than 1.0.
- This stopping rule will be applied whenever an unblinded evaluation is done, and a total of 30 or more infusion cycles have been administered.
- For the first 30 infusion cycles a fixed rule was applied by the IDMC to temporary suspend study drug administration in case the number of related serious TEEs or acute renal failures as assessed by IDMC in the Panzyga group was twice the number in the placebo group. If no TEE or acute renal failure was observed in the placebo group during this initial study phase, temporary suspension of study drug administration and safety investigation was initiated if two related serious TEEs as assessed by IDMC or acute renal failures had been reported in the Panzyga group.

Regulatory authorities and IECs/IRBs should be informed in accordance with national regulations.

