**Test Product, Dose, and Mode of Administration:**

Panzyga is a 10% solution of IVIG ready for intravenous (IV) administration. The product is delivered as ready-to-use solution in glass bottles. Panzyga should be stored and transported light-protected at +2°C to +8°C (36°F to 46°F) and must not be frozen.

Patients are randomly assigned (1:1) to Panzyga or placebo as initial treatment arm. In the Panzyga arm, Panzyga will be administered in a dose of 1 g/kg body weight (BW) daily for two consecutive days, and if tolerated, administered in three-week intervals up to nine weeks

Name of Sponsor/Company: Octapharma Pharmazeutika Produktionsges.m.b.H.	
Name of Investigational Product: Panzyga	Protocol Identification Code: NGAM-13
Name of Active Ingredient: Immune Globulin Intravenous, Human 10%	Date of Final Protocol: 21 July 2023

(total Panzyga exposure 6 g/kg BW). After completion of the first phase of the study, blinded crossover assignment will be done: patients previously in the Panzyga arm will be assigned placebo and patients previously in the placebo arm will be assigned Panzyga, administered at the same regimen.

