### 3.2 Overall Study Design and Plan

The study is planned to start in Q3 2021 and to be clinically completed by Q4 2024. The study will be a prospective, multicenter, randomized, double-blind, parallel group, placebo-controlled, Phase III superiority study in a minimum of █ pediatric patients with confirmed diagnosis of moderate to severe PANS with prominent and stable OCD symptoms (i.e. CGI—Severity-OCD rating of  $\geq 4$  or higher on 2 ratings without a change of more than 1 unit between measurements). The study includes an additional double-blind, crossover safety and efficacy follow-up phase of three infusions of Panzyga or placebo administered over 2 days every three weeks for a total of nine weeks.

[figure not shown]
After the first █ patients had been enrolled, the study enrollment was put on hold to further enhance the safety monitoring of Panzyga administration. The study resumed only after the Independent Data Monitoring Committee (IDMC) had reviewed unblinded safety and PK data of these █ patients and given the green light to pursue the study.

Up to 30 sites are projected to participate in this clinical study.

Eligible patients will be randomized 1:1 to two possible treatment sequences:

- (Panzyga – Placebo): three administration cycles with Panzyga, followed by three administration cycles with placebo
- (Placebo – Panzyga): three administration cycles with placebo, followed by three administration cycles with Panzyga

Patients will undergo repeated efficacy and safety assessments relating to each cycle. After completion of the first double-blind treatment period, blinded crossover assignment will be done; patients previously in the Panzyga arm will be assigned placebo and patients previously in the placebo arm will be assigned Panzyga, administered at the same regimen. Figure 1 depicts the study design. Rescreening is allowed for patients who were eligible based on the onset of symptoms, but have recently initiated CBT, psychotropic medication, corticosteroids, anti-virals, or antibiotics, provided these treatments are completed within the timelines stated in the exclusion criteria (Section 4.1.2).

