### **4.4 Assignment of Patients to Treatment Sequences**

Patients will be identified by unique codes, including the site identification number and a sequence number assigned by an electronic system in strict order of enrollment. Randomization will be managed centrally by means of an interactive response technology (IRT) system and ensure balanced allocation of the patients to the two randomization arms within the defined strata. The fact that a patient has been randomized will be reported immediately and automatically to the investigator, the contract research organization (CRO) and the Sponsor.

Randomized patients are not permitted to re-enroll under any circumstance.

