As discussed, for added safety monitoring, enrollment was be paused after the first █ patients have been randomized and enrolled in the study, for a planned IDMC review of unblinded safety and PK data, including IgG trough levels. Enrollment resumed only after IDMC data review of the first █ patients had been completed, and the IDMC had recommended to continue enrollment in the study. In addition, after █ patients have completed blinded treatment (Visit Week 9), an interim review of the preliminary safety and efficacy data will be conducted by IDMC. At this timepoint, the IDMC will independently evaluate all data accrued in this pivotal study to provide a statement on whether emerging data confirm the prospect of direct benefit and positive risk-benefit ratio for PANS patients treated with Panzyga. IDMC confirmation will justify the submission to concerned Health Authorities of the additional study protocol(s) evaluating other dose regimens of Panzyga treatment in patients with PANS. The actual numeric results will not be shared with the Sponsor or Investigators to ensure that bias will not affect subsequent study decisions since the data of the first █ patients will be included in the final statistical analysis. Details will be provided in the IDMC Charter.

In addition to the ongoing safety monitoring and periodic IDMC data review, study drug administration will be temporarily suspended, pending a safety investigation, in the event of an unacceptable increase in any AE the Panzyga group compared to the placebo group, with particular emphasis on TEEs and HTRs.

As specified by the EMA and the FDA, safety evaluation will include monitoring of short-term tolerance (blood pressure, heart rate, temperature, and monitoring of other AEs) at repeated intervals following IVIG infusion. All AEs that begin during or within 72 hours after an infusion will be classified and analyzed as infusional AEs. Adverse events will be evaluated with regard

to the infusion rates [57, 63]. The safety evaluation will also include a measure of suicidal ideation (C-SSRS), as recommended by the FDA for drug trials in patients with psychiatric symptoms [64].

A pre-treatment serum sample and one at the end of the study from each patient included in the clinical study will be stored at -70 °C for possible future testing [63].

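### The suspension rule for venous thromboembolism and acute renal failure aims at Panzyga versus placebo, but its formula tallies by randomization arm with no Week 9 cut-off, so a literal tally dilutes the ratio after crossover

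*Protocol*

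**What the plan says.** Protocol 6.2.2 (Premature Termination of the Study) sets out a temporary suspension of dosing "for an unacceptable increased venous TEE or acute renal failure risk in the Panzyga group compared to the placebo group". It labels the quantity of interest as the Panzyga risk over the placebo risk. The sentence that defines the calculation reads "the event risk will be calculated separately as (number of events reported)/(number of infusions) in both randomization arms". The rule triggers when the lower 90% confidence limit for the ratio exceeds 1.0. A zero-event provision applies: "In case no Events are observed in the placebo group, 1 will be added to each cell in the 2X2 table".

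On timing, "This stopping rule will be applied whenever an unblinded evaluation is done" and at least 30 infusion cycles have been given. Nothing limits the tally to data before Week 9, and nothing says which product an event or infusion belongs to.

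Protocol 4.4 uses the same term for allocation: central randomization is to "ensure balanced allocation of the patients to the two randomization arms within the defined strata", under a section title that refers to treatment sequences. Protocol 3.2 defines those sequences as three cycles of one product followed by three of the other.

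SAP 8.4 groups safety data by exposure (Panzyga, Placebo, Placebo after Panzyga) because of the crossover, but for summaries. SAP 6.2 refers the reader to the protocol for the exact stopping criteria.

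**The concern.** After Week 9 neither randomization arm is a single-product group. Under a literal tally, the Panzyga events of the Placebo–Panzyga sequence fall on the placebo side. The placebo infusions of the other sequence enlarge the Panzyga denominator. Both effects pull the ratio toward 1 as crossover data build up, while children are still being dosed.

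This is the only suspension rule in the readable text that has a formula. If it is programmed as written, it can report no excess when there is one. Even someone who sees that a tally by product was meant finds no instruction on whether post-crossover placebo infusions join the comparator, or where late events after Panzyga belong.

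**Working it through.** The documents give no operating characteristic for this rule, so there is no stated figure to reproduce.

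**Inputs from the documents.** 1:1 allocation (Protocol 3.2); two infusions per cycle and three cycles per phase, so 6 infusions per patient per phase (5.4); 90% limit and +1-per-cell step (6.2.2); 10% dropout (Study Outline, Number of Patients).

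**Assumed.** 60 patients in total (sample size is redacted), event risks per infusion, and equal f in both sequences. f=0.9 represents the 10% dropout, taken to occur before phase 2.

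**Dilution of the ratio.** Let r be the placebo risk per infusion, Rr the Panzyga risk, n the phase-1 infusions per sequence and fn the phase-2 infusions, with no carry-over.

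- Panzyga–Placebo arm: expected events nRr + fnr, over n(1+f) infusions.
- Placebo–Panzyga arm: expected events nr + fnRr, over n(1+f) infusions.
- By-arm ratio = (R+f)/(1+fR).

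| True R | f=0.5 | f=0.9 | f=1 |
|---|---|---|---|
| 3 | 1.40 | 1.05 | 1.00 |
| 5 | 1.57 | 1.07 | 1.00 |
| 10 | 1.75 | 1.09 | 1.00 |

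For example, (5+0.5)/(1+2.5) = 1.57. These values need no assumed event rate or sample size.

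**A concrete table.** Assume 40 patients per arm, both phases complete, 5 Panzyga events in each phase and no placebo events. By arm this is 5/480 versus 5/480: ratio 1.0, lower limit 0.36, no trigger. By product it is 10/480 versus 0/480: ratio 11.0 after adding 1 to each cell, lower limit 1.98, trigger.

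**Trigger probability.** Log-scale Wald limit with z=1.645, +1 per cell when the placebo side has no events, exact binomial sums. With 60 patients there are 30×6 = 180 phase-1 infusions per sequence, plus 90 (f=0.5) or 162 (f=0.9) in phase 2.

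| Risk per infusion | f | By arm | By product, all placebo | By product, Placebo after Panzyga dropped | Week 9 data only |
|---|---|---|---|---|---|
| 2% vs 0.2% | 0.5 | 0.10 | 0.53 | 0.15 | 0.24 |
| 2% vs 0.2% | 0.9 | 0.04 | 0.70 | 0.13 | 0.24 |
| 1% vs 0.2% | 0.5 | 0.020 | 0.097 | 0.005 | 0.027 |
| 1% vs 0.2% | 0.9 | 0.015 | 0.18 | 0.002 | 0.027 |
| 0.5% vs 0.1% | 0.5 | 0.002 | 0.010 | 0.0001 | 0.002 |

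With no crossover data every tally equals the last column. At 0.5% versus 0.1% the by-arm figure is 0.002 at f=0, 0.5 and 0.9. A risk of 2% per infusion is extreme: 1−0.98^6 = 0.114, or about 11% of children over six infusions.

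**Why the comparator matters.** With zero placebo events and equal denominators, 5 Panzyga events trigger the rule: at 180 versus 180, (6/182)/(1/182) = 6.0, lower limit 1.02. If Placebo after Panzyga is dropped, 270 versus 180 infusions needs 8 events, (9/272)/(1/182) = 6.02. At 342 versus 180 it needs 10, (11/344)/(1/182) = 5.82.

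**False triggers.** At a true ratio of 1 the by-arm and all-placebo tallies coincide. For risks of 0.2% to 0.5% the probability is 0.0001 to 0.004 at f=0.5 and 0.0004 to 0.008 at f=0.9.

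**Carry-over.** If post-crossover placebo infusions carry c times the placebo risk, the all-placebo ratio is R(1+f)/(1+fc) and the by-arm ratio is (R+fc)/(1+fR). For R=5 and c of 2 to 3, the all-placebo tally reads 3.75 to 3.00 at f=0.5 (by arm 1.71 to 1.86) and 3.39 to 2.57 at f=0.9 (by arm 1.24 to 1.40).

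**The case against.** The strongest reply is that nobody would count this way. The same rule names a Panzyga group and a placebo group and labels the ratio by product; after crossover a by-sequence tally has no Panzyga risk to put in the numerator. Elsewhere an arm is a status that patients leave: "patients previously in the Panzyga arm will be assigned placebo and patients previously in the placebo arm will be assigned Panzyga", and "Patients are randomly assigned (1:1) to Panzyga or placebo as initial treatment arm". SAP 8.4 and SAP 11 go by exposure, and the IDMC Charter and Protocol 9.2.3 and 9.3, which cannot be read, may define the groups. All of this stands as evidence of intent. A reader might infer that the IDMC is miscounting events; the documents do not show that.

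It does not remove the conflict. Protocol 4.4 uses the term for allocation, and SAP 6.2 points back to the sentence at issue.

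A second reply is that little sensitivity is lost in practice. This is partly right. At 1% versus 0.2% the by-arm probability moves only from 0.027 with no crossover data to 0.020 and then 0.015; the rest of the gap to 0.097 or 0.18 is power gained by using phase-2 data correctly. At 0.5% versus 0.1% it does not fall at all. So the tempting general claim, that the rule's chance of triggering falls as data accrue, is not supported; what holds generally is that the ratio is diluted.

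Third, the rule is a backstop. TEEs are reported as SAEs within 24 hours (7.3.4, 7.3.5), the IDMC reviews them promptly (8.6.2), and 7.5 separately commits to suspension "in the event of an unacceptable increase in any AE the Panzyga group compared to the placebo group". These safeguards remain and limit the harm.

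Finally, the choice of comparator and of a carry-over window is a design decision, since SAP 8.4 deliberately separates Placebo after Panzyga. That is accepted.

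**Conclusion.** The point holds as a conflict between a rule's wording and its stated purpose. Followed literally after crossover, the formula in 6.2.2 moves any true ratio above 1 toward 1, reaching 1.00 when phase-2 and phase-1 infusions are equal. That result is algebraic, given equal f in both sequences, constant risks and no carry-over.

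The consequence for triggering depends on assumed sample size and risks. It is large only at high event risks (0.10 by arm against 0.53 by product with all placebo infusions, at 2% versus 0.2% and f=0.5), small at 1%, and immaterial at 0.5%, where no tally has useful power. It should be fixed because the rule protects children during dosing and the edit is simple. Confidence is medium, because the Charter could already settle the grouping.

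**What to change.** In Protocol 6.2.2, replace the reference to randomization arms with a tally by IMP received: each infusion counted under the product infused, each event under the product being received at onset. Put the same text in the IDMC Charter and the same grouping in the IDMC programs.

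The IDMC should also state how post-crossover placebo is handled. Including all placebo infusions in the comparator is recommended, with Placebo after Panzyga shown separately as a supporting display. Dropping it while keeping the +1-per-cell step raises the smallest trigger from 5:0 to 8:0 (f=0.5) or 10:0 (f=0.9) and loses most or all of the gain.

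Whether events soon after the last Panzyga infusion stay with Panzyga, for example for the 21 days of SAP 8.4, is for the sponsor and IDMC to decide. On the nominal schedule that window runs from Week 6 day 2 to Week 9 day 2, so it overlaps the cycle-4 placebo infusions; this is why infusions should be counted under the product infused.

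The cost is one or two sentences and no new data. If the IDMC already counts by product with all placebo infusions, only the wording changes. The downside is some dilution if risk carries over into post-crossover placebo.
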